6.2.2 Treatment period

After Visit 1, the patient will return for 51 additional visits during the treatment period. The duration between visits is 4 weeks. At every visit study drug will be administered.

If the patient completes this 4 year study, the last study drug administration will be at Visit 52 (EOT).

Drug administration and rules for early/late visits

It's important for the patient to adhere to the visit schedule per the [Flow Chart](#). The visit schedule should always align with Visit 1.

The IRT system has been set up to make sure that a patient does not receive 2 doses of medication in less than a 14 day period.

In these scenarios, the patient should conduct the visit but skip the dose. The patient should be administered the dose at the next scheduled visit.

Pregnancy Testing

Urine pregnancy testing for all woman of childbearing potential will be conducted on-site prior to every dosing and must be negative to receive study drug. A positive urine test must be confirmed with a serum pregnancy test at the central laboratory.

See the [Flow Chart](#) for details of all procedures required at each visit.

Unscheduled visits

If a patient suspects that their AD is worsening in between the protocol specified scheduled visits, they should make an unscheduled visit and return to the clinic/site for assessment. The patient may be called in for additional unscheduled visits due to safety reason at the discretion of the investigator or the sponsor, unless the patient has withdrawn his/her consent. The patient may also contact the site due to safety reason for an unscheduled visit. The unscheduled visit may include additional collection of blood samples for safety reasons. The unscheduled visit may also include additional assessments deemed necessary by the investigator such as laboratory samples, ECGs, or other procedures which were missed at a previous visit. All unscheduled visits should be described (including the reason for the visit) and documented in the medical/source record, and in the eCRF.

6.2.3 End of Treatment and Trial Completion

For all treated patients termination of trial medication and trial completion must be recorded on the corresponding eCRF.

For the comprehensive list of the trial procedures required at the EOT and the EOS visits please refer to [Flow Chart](#).

The EOS visit must be performed 16 weeks after the date of last drug administration.

Early Treatment and Trial Discontinuation:

If trial treatment is discontinued prematurely prior to the planned [Flow Chart](#) EOT visit, every effort should be made to have the patient return and undergo the procedures for the EOT visit as well as the EOS visit 16 weeks after the last study drug administration as outlined in the [Flow Chart](#).

Patients who are unable to physically return to the study site for the EOT and EOS visits should be contacted by the site by phone to collect information pertaining to adverse events and changes to concomitant therapy.

Trial Completion:

Trial completion is defined as a patient having reached the EOS visit within the specified window per protocol.

Treatment Completion:

Treatment completion is defined as a patient completing Visit 52 which is the EOT visit after receiving approximately 4 years of treatment

7. STATISTICAL METHODS AND DETERMINATION OF SAMPLE SIZE

This is an exploratory extension trial in patients with AD. It is designed as an open label study with one group of BI655130 150mg/mL (600mg once every four weeks).

The primary objective of this trial is to assess the long term safety and efficacy of treatment with BI 655130 in patients with AD who have completed and have responded to treatment in the parent study 1368-0032.

The primary endpoint is the number of patients with treatment emergent adverse events (AEs) at week 48. The efficacy will be assessed using secondary and further endpoints.

All analyses are planned to be descriptive in nature.

7.1 NULL AND ALTERNATIVE HYPOTHESES

No statistical testing is planned for this study. Only descriptive analyses are intended. Therefore, no statistical hypotheses are defined.

7.2 PLANNED ANALYSES

7.2.1 General considerations

The efficacy analyses will be performed for the Full Analysis Set (FAS) that includes all patients who entered the study, received at least one dose of treatment, had a baseline measurement, and at least one post-baseline measurement.

All safety analyses will be performed on patients who entered the study and received at least one dose of treatment during the trial. This set of patients is called Safety Analysis Set (SAF).

With regard to efficacy and safety endpoints “baseline” refers to:

1. Baseline for the parent trial – the measurement recorded at randomisation visit (Visit 2) of the parent trial (1368-0032). If the data at Visit 2 is missing, then the data from Visit 1 of the parent trial will be considered baseline.
2. Baseline for the extension trial – the last measurement before the BI655130 treatment intake in this extension trial.

Two separate analyses will be conducted – one including baseline from parent trial and the second including baseline from this extension trial.

Important deviations of the protocol will include key inclusion and exclusion deviations, incorrect medication taken, concomitant use of restricted medications, and any other deviations from the protocol deemed important by the study team.

This is an exploratory trial and sensitivity analyses may need to be done to investigate the effects of potential confounding factors.

Standard statistical parameters (number of non-missing values, mean, standard deviation (SD), median, quartiles, minimum and maximum) of frequency tables (including patient frequencies and percentages) will be calculated where appropriate.

The statistical parameters will be provided for the following groups:

1. By treatment received in the parent trial (1368-0032):
 - Placebo followed by BI655130 treatment
 - Placebo followed by no BI655130 treatment
 - BI655130 followed by BI655130 treatment
 - BI655130 followed by no BI655130 treatment
 - Total
2. By the response achieved at week 16 of the parent trial (1368-0032):
 - Responders – patients who attained at least 75% reduction in EASI score at week 16 compared to baseline during the parent trial
 - Non-responders - patients who attained less than 75% reduction in EASI score at week 16 compared to baseline during the parent trial;
 - Total

7.2.2 Primary endpoint analyses

The primary endpoint is the number of patients with treatment emergent AEs at week 48 and will be a part of the safety analysis (as described in [Section 7.2.5](#)). The primary analysis will be descriptive and will result in frequency table presenting the numbers and percentages of patients with treatment emergent AEs displayed per group as defined in [Section 7.2.1](#) and also by the following subgroups:

- Asian/Non-Asian
- Age groups: <=30 years old/>30 years old

The primary analysis will be performed on the SAF.

[figure not shown]
7.2.3 Secondary endpoint analyses

All secondary analyses are planned to be descriptive. For continuous endpoints (change from baseline in EASI score and in SCORAD), standard statistical parameters (including number of non-missing values, mean, SD, median, quartiles, minimum, and maximum) will be presented per group as defined in [Section 7.2.1](#) and also by the following subgroups:

- Asian/Non-Asian
- Age groups: <=30 years old/>30 years old

For the EASI score, responder analyses will be performed. A patient is defined as EASI50 or EASI75 responder when percent change from baseline in EASI score is at least 50% or at least 75%, respectively. This results in binary variable with values of 1 (=responder) or 0 (=non-responder).

For binary endpoints (EASI50, EASI75, achieving at least a 2-grade reduction from baseline to clear (0) or almost clear (1) in IGA), frequency tables with numbers and percentages of patients will be used and display relevant categories in groups as defined in [Section 7.2.1](#).

7.2.5 Safety analyses

Adverse events will be coded using the Medical Dictionary for Drug Regulatory Activities (MedDRA). Standard BI summary tables and listings will be produced. All adverse events with an onset between start of treatment and end of the REP, a period of 16 weeks after the last dose of trial medication, will be assigned to the on-treatment period for evaluation.

All treated patients will be included in the safety analysis. In general, safety analyses will be descriptive in nature and will be based on BI standards. No hypothesis testing is planned.

Statistical analysis and reporting of adverse events will concentrate on treatment-emergent adverse events, i.e. all adverse events occurring between start of treatment and end of the REP. Adverse events that start before first drug intake and deteriorate under treatment will also be considered as 'treatment-emergent'.

Frequency, severity, and causal relationship of adverse events will be tabulated by system organ class and preferred term after coding according to the Medical Dictionary for Drug Regulatory Activities (MedDRA).

Laboratory data will be analysed both quantitatively as well as qualitatively. The latter will be done via comparison of laboratory data to their reference ranges. Values outside the reference range as well as values defined as clinically relevant will be summarised. Groups (defined in [Section 7.2.1](#)) will be compared descriptively with regard to distribution parameters as well as with regard to frequency and percentage of patients with abnormal values or clinically relevant abnormal values.

Vital signs, physical examinations, or other safety-relevant data observed at baseline, during the course of the trial and at the end-of-trial evaluation will be assessed with regard to possible changes compared to findings before start of treatment.

[REDACTED]

7.2.7 Interim Analyses

In order to ensure the patient's safety during the trial, an external DMC, independent of the trial and project teams, will be set-up to review all available safety data as well as selected efficacy data at regular intervals following first-patient-in. A DMC SAP which describes the analyses required for assessment by the DMC will be produced and finalised prior to first patient included into the trial. Further details will be provided in a DMC charter.

There will not be an interim analysis from a statistical standpoint.

As the primary aim of this study is to collect long-term safety and efficacy data on the use of BI655130 in this population, multiple status reviews will be done over the approximate 4-year conduct phase of this trial to support, for example, regulatory interactions, CTA and MAA/BLA submissions, but also to provide important safety and efficacy information to the sponsor to guide further development of the compound, and to investigators via IB updates and publications. Status review analyses will be performed on demand and are not feasible to be pre-defined.

A CTR describing all data collected within this trial will be produced once the last patient in the trial has completed the final End-of-Study (EOS) visit.

7.3 HANDLING OF MISSING DATA

Every effort will be made to collect complete data at all visits. However, missing data will still occur and approaches to handle this are proposed below.

With respect to safety or continuous efficacy evaluations, it is not planned to impute missing values.

For all binary endpoints (i.e. endpoints that are either 1 (patient responded) or 0 (patient did not respond)), the following rules apply:

- If there are data at visits both before and after the visit with a missing outcome, then impute as responder only if both neighbouring visits also represent a responder;
- Otherwise, impute as a non-responder.

For disease specific protein markers the following handling of data below or above the limit of quantification will be applied:

- Below limit of quantification (BLQ) data will be replaced by 0.5 times the lower limit of the quantification (LLOQ)
- Above limit of quantification (ALQ) data will be replaced by upper limit of quantification (ULOQ), if ULOQs are available. Otherwise, ALQ data will be excluded from the analysis.

Further sensitivity analyses to assess the robustness of the results may be performed and as such will be described in the TSAP.

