5.7 APPROPRIATENESS OF MEASUREMENTS

The safety assessments are standard, are accepted for evaluation of safety and tolerability of a SC administered drug, and are widely used in clinical trials. The pharmacokinetic parameters and measurements outlined in [Section 5.3](#) are generally used assessments of drug exposure. The biomarker parameters outlined in [Section 5.4](#) are of exploratory nature only.

Information about race should be obtained from all study participants as allowed by local regulations. This is because the prevalence and characteristics of AD may differ between patients of different racial origin. It will thus be worthwhile to assess if patients of different race will respond differently to the study treatment.

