3. INTRODUCTION

As per ICH E9 (1), the purpose of this document is to provide a more technical and detailed elaboration of the principal features of the analyses described in the CTP and its amendments, and to include detailed procedures for executing the statistical analysis of the data.

This trial statistical analysis plan (TSAP) assumes familiarity with the CTP. In particular, the TSAP is based on the planned analysis specification as written in CTP Section 7 “Statistical Methods and Determination of Sample Size”. Therefore, TSAP readers may consult the CTP for more background information on the study, e.g., on study objectives, study design and population, treatments, definition of measurements and variables, planning of sample size, randomisation.

A separate Biomarker Statistical Analysis Plan (BM-SAP) will complement this TSAP.

Pharmacokinetic (PK) parameters are not planned to be analysed nor be the part of the CTR.

The statistical analyses will be performed within the validated working environment CARE, including SASTM (current Version 9.4, by [REDACTED]), and a number of SASTM-based tools (e.g., macros for the analyses of AE data or laboratory data; Report Appendix Generator system (RAGe) for compilation/formatting of the CTR appendices).

This TSAP will document the features of the data that will be performed for a final analysis. The specifications of the analyses for the status reviews at the time points within the requested timelines will be defined as requests in the Cumulative Statistical Analysis Plan (CSAP).

The results of the analyses defined in this SAP will be summarised in the abbreviated CTR.

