7. PLANNED ANALYSIS

All efficacy and safety analyses will be purely exploratory in nature. The following analyses are planned throughout the trial.

- **Status review (at the requested timelines)**

The status reviews will be performed periodically and on demand. The analyses will include all data available at the time of the snapshot. The analyses are planned to be defined for each time point as requests in the CSAP, depending on the requirements.

- **Final analysis (Week 220)**

The analysis of the entire efficacy, safety, PK, and biomarker data collected through the full 220 weeks of follow-up will be performed once all entered patients have completed the trial (up to EoS Visit); at that time point, a final database lock will be done and all data through week 220 will be reported. The majority of biomarkers will be reported outside the CTR.

General Remarks

The format of the listings and tables will follow the BI guideline “Standards for Reporting of Clinical Trials and Project Summaries” [BI-KMED-BDS-HTG-0045] (7) with the exception of those generated for PK.

The individual values of all patients will be listed, including those collected during the off-treatment period. Listings will generally be sorted by country, centre number, patient number and visit (if visit is applicable in the respective listing). AE listings will be sorted by treatment (see [Section 7.8.1](#) below for details).

The following standard descriptive statistical parameters will be displayed in summary tables of continuous variables:

N	number of non-missing observations
Mean	arithmetic mean
SD	standard deviation
Min	minimum
Q1	lower quartile
Median	median
Q3	upper quartile
Max	maximum

The data format for descriptive statistics of concentrations will be identical with the data format of the respective concentrations.

Statistical parameters will be displayed to a defined number of decimal places as specified in the BI guideline “Standards for Reporting of Clinical Trials and Project Summaries” (7).

Tabulations of frequencies for categorical data will include all possible categories and will display the number of observations in a category as well as the percentage (%) relative to the respective treatment. Percentages will be rounded to one decimal place. The category missing will be displayed if and only if there actually are missing values. Percentages will be based on all patients in the respective patient set whether they have non-missing values or not.

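### Protein-marker values above the quantification limit are dropped when no ULOQ is available, so marker levels are biased downward at the visits affected (exploratory markers only)

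*Protocol*

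**What the plan says.** Protocol 7.3 (Handling of missing data) opens the rule with its scope: "For disease specific protein markers the following handling of data below or above the limit of quantification will be applied". Three branches follow.

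- Below the limit: the value stays in the analysis at half the LLOQ.
- Above the limit, ULOQ known: "Above limit of quantification (ALQ) data will be replaced by upper limit of quantification (ULOQ), if ULOQs are available".
- Above the limit, ULOQ not known: "Otherwise, ALQ data will be excluded from the analysis".

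The section closes with an optional provision: "Further sensitivity analyses to assess the robustness of the results may be performed and as such will be described in the TSAP".

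SAP 6.6, on missing data, has no rule for values outside the quantification range, and the public SAP text describes no sensitivity analysis for them. SAP 6.7 assigns biomarker measurements to visit windows, and SAP 7 includes biomarker data in the final analysis. SAP 3 adds: "A separate Biomarker Statistical Analysis Plan (BM-SAP) will complement this TSAP". That plan is not among the documents.

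On the standing of these data, Protocol 5.7 says the biomarker parameters "are of exploratory nature only", and SAP 7 says: "The majority of biomarkers will be reported outside the CTR".

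**The concern.** A result above the limit is censored, not missing: the assay shows that the level is high but not how high. The third branch treats it as if nothing were known. Because being high is what triggers the loss, the remaining values are a sample with its upper tail cut off. The low end gets no such treatment, so the rule is also lopsided.

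There are two consequences. At a visit with an excluded value, the mean, median and quartiles of the marker are too low. In the change from baseline, a patient with an ALQ baseline is lost at every later visit, and a patient whose on-treatment value is ALQ is lost at that visit. The first had the highest starting level; the second is one whose marker stayed high or rose. In a summary table an excluded value looks like an absent sample, so a reader could not see that this had happened.

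**Working it through.** **No figure to reproduce.** The documents give no ALQ rate, marker distribution or list of markers without a ULOQ. Everything below is an illustration under stated assumptions.

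**Assumptions.** Log marker at baseline b ~ N(0, 1). On treatment t = −ln 2 + 0.7b + √0.51·e with e ~ N(0, 1), so the geometric mean is halved and the correlation is 0.7. The same limit u = z(1−q) applies at both visits, with q = 5%, 10% or 20% of baseline values above it. No ULOQ is available.

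**Baseline level under exclusion (closed form).**

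- Raw mean = e^0.5 · Φ(u−1)/(1−q), against a true e^0.5 = 1.65.
 - q = 5%: 1.649 × 0.7405/0.95 = 1.285 (22% low)
 - q = 10%: 1.649 × 0.6109/0.90 = 1.119 (32% low)
 - q = 20%: 1.649 × 0.4371/0.80 = 0.901 (45% low)
- Median = exp(z((1−q)/2)), against a true 1.00.
 - q = 5%: exp(−0.063) = 0.94
 - q = 10%: exp(−0.126) = 0.88
 - q = 20%: exp(−0.253) = 0.78

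**Change from baseline (simulation, 2,000,000 pairs; under exclusion a pair is lost if either value is ALQ).** The true raw mean change is 0.5 × 1.649 − 1.649 = −0.824, the true log change is −0.693, and the true median percent change is −50%.

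| | 5% ALQ | 10% ALQ | 20% ALQ |
|---|---|---|---|
| Pairs lost | 5.4% | 10.8% | 21.5% |
| Lost out of 40 patients | 2.1 | 4.3 | 8.6 |
| Raw mean change, excluded | −0.582 (71%) | −0.485 (59%) | −0.366 (44%) |
| Raw mean change, capped at limit | 82% of true | 72% | 56% |
| Log change, excluded | −0.666 (96%) | −0.646 (93%) | −0.614 (89%) |
| Log change, capped | −0.675 | −0.654 | −0.608 |
| Median % change, excluded | −48.6% | −47.5% | −45.6% |
| Median % change, capped | −49.0% | −47.7% | −44.3% |

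The 40 is the approximate planned number in Protocol 7.5. Capping at the limit stands in for keeping ALQ values at the highest quantified value.

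**What retention does to the visit summary.** If ALQ values keep the top rank, the visit median stays at 1.00 while fewer than half the values are ALQ. On the log scale the baseline mean is low by 0.11, 0.19 and 0.35 SD under exclusion, against 0.02, 0.05 and 0.11 SD under capping.

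**A case with no bias in change.** With no true change and the same spread at both visits, exclusion leaves the mean change unbiased. Levels are still too low, and at 10% ALQ per visit 15% to 17% of pairs (6 to 7 of 40) are lost for correlations of 0.7 and 0.5.

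**The case against.** The strongest reply is that this is a fallback within an exploratory analysis. ALQ values are normally kept at the ULOQ; exclusion applies only where no ULOQ exists, and the documents do not show that any marker is in that position. The biomarker plan may already refine the rule, and the biomarker sections of the protocol are not in the public text, so neither the assays nor the analysis scale can be seen. Medians, quartiles and counts of non-missing values are already listed in Protocol 7.2.1 and SAP 7. All of this stands, and it limits the importance. It does not make the exclusion rule sound: the protocol states the rule outright, and the biomarker plan is described only as a complement to the SAP. The planned medians would be taken after deletion, and the planned counts do not separate excluded from absent values.

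Three stronger readings are tempting, and the documents or the arithmetic do not support them.

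- *That the trial's evidence on disease activity is compromised.* That evidence is EASI, SCORAD and IGA, the secondary endpoints, and the primary endpoint is treatment-emergent adverse events. The rule touches none of them.
- *That change from baseline shrinks to around half.* This holds only for raw-scale means of a skewed marker, where the upper tail dominates. On the log or percent scale, most of the change survives.
- *That retaining the values repairs the change from baseline.* On the log and percent scales capping does about as well as exclusion, and slightly worse at 20% ALQ.

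**Conclusion.** The point holds as a minor but genuine flaw in the analysis rule. Wherever an ALQ value is excluded, the marker level at that visit is biased downward and the patient drops out of the change from baseline. The bias in level is certain in direction. The bias in change depends on how ALQ rates differ between baseline and follow-up, and is towards understating a fall when the marker truly falls.

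The size is unknown. Under the assumed model with 5% to 20% of baseline values ALQ, the baseline median is 6% to 22% too low and about 5% to 22% of pairs are lost. Mean change keeps 71% down to 44% of its true size on the raw scale, but 96% down to 89% on the log scale. These figures rest on the log-normal shape, log-SD 1, correlation 0.7, a halved geometric mean and the assumed ALQ rates. With no ALQ values, or with a ULOQ for every marker, exclusion has no effect. No primary or secondary result changes.

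**What to change.** Replace the exclusion sentence in Protocol 7.3 with:

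> If the ULOQ is not available it will be requested from the assay laboratory. If it cannot be obtained, ALQ values are retained as the highest rank (set to the highest quantified value for that marker). Marker levels at visits with ALQ values are summarised primarily by median and quartiles, and the number and percentage of ALQ values is shown at each visit.

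Align the biomarker plan if it does not already do this.

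The cost is a few sentences and one extra line in the marker tables; no patient, visit or sample is affected. The limits should be stated with the rule. Substitution keeps the visit median correct while fewer than half the values are ALQ, but means remain somewhat low. Change from baseline, mean or median, stays attenuated, on the log or percent scale about as much as under exclusion. Change results for affected markers should therefore be flagged as censored.
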